15 STATISTICS

The statistical planning and evaluation of the study will be carried out by a qualified statistician in accordance with the International Conference on Harmonisation (ICH) guidelines and adequate biostatistics standard operating procedures (SOPs). A detailed Statistical Analysis Plan (SAP) will be prepared prior to database closure and unblinding.

15.1 Calculation of Sample Size

Sample size was not based on any statistical assumptions, as no formal statistical tests are planned. Approximately 36 subjects will be treated in the study and provide sufficient efficacy and safety information of study medication.

15.2 Statistical Methods

15.2.1 Populations for Analysis

Three analysis sets will be defined for analysis:

Safety set:

The safety set comprises all subjects who have received the study medication at least once.

Intention-to-treat set:

The intention-to treat (ITT) set consists of all subjects who have received any study medication and have at least 1 post-baseline efficacy measurement.

Per-protocol set:

The per-protocol (PP) set consists of all subjects of the ITT set who finish the study without major protocol deviations or who discontinue the trial prematurely due to an event which could be possibly related to the study medication. Subjects with major protocol deviations will be excluded from the PP population. Classification of protocol deviations as major or minor will be agreed upon between Sponsor and study statistician prior to the analysis.

Pharmacokinetic set:

The pharmacokinetic (PK) set will include all subjects who have at least one dose of study drug without major protocol deviations and for whom the serum concentrations of BT063 are interpretable. It will be used for the pharmacokinetic analysis.

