11.5 Prohibited Medication or Treatment

Medication other than allowed SLE treatments that is considered necessary for the subject's safety and well-being may be given at the discretion of the investigator and recorded in the appropriate sections of the eCRF. Investigators are encouraged to discuss the introduction of any restricted medications with the Sponsor or its representative.

Medications that are restricted or have special allowances during the study are listed in [Table 11.1](#). These restrictions begin at screening and are to be followed through the End of Treatment Visit at W14. During the 14-week follow-up period, certain medications may be administered at the investigator's discretion. However, no new medications for SLE should be started at any time during the study.

Table 11.1: Treatment Restrictions

Treatment	Restriction or Allowance
Glucocorticosteroids:	
Oral Glucocorticosteroids: stable dose \leq 20.0 mg prednisone daily or equivalent for at least 2 weeks prior to baseline and through the End of Treatment Visit at week 14. At most two short courses of an increased dose of oral glucocorticosteroids (i.e., 5 days) are allowed between week 4 and week 12 for management of flares. During the follow-up period these medications may be administered at the investigators discretion.
 
Intramuscular or intra-articular Glucocorticosteroids: not permitted in the 4 weeks prior to screening and during the entire study. If necessary, 1 intra-articular steroid injection is allowed, but the treated joints cannot be assessed within 4 weeks.
 
Intravenous Glucocorticosteroids (pulse therapy): not allowed within the 6 months before screening and during the entire study.
 
Inhaled and topical Glucocorticosteroids: use of topical steroids is allowed, but not within 24 hours before assessment.

Antimalarial drugs: hydroxychloroquine/ chloroquine	Stable dose levels up to the highest dose defined by the SPC for treatment of SLE are allowed during the 8 weeks prior to baseline and through the End of Treatment Visit at week 14. During the follow-up period these medications may be administered at the investigators discretion.

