Not related:	Adverse events for which a reasonable explanation for an alternative cause is considered plausible, e.g., no study drug taken, plausible clinical alternative like accidental injury, expected progression of underlying or concomitant disease, pharmacologically incompatible temporal relationship, or intercurrent illness.
Related:	Adverse events for which a reasonably possible clinical and/or pharmacological relationship to study drug cannot be excluded, e.g., lacking plausible alternatives.

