15.2.5 Efficacy Analysis

The efficacy endpoints in this study are as below:

- 50% improvement of swollen/tender joints or 50% improvement in CLASI score at week 14 and at week 28, depending on which endpoint was the more severe manifestation at baseline.
- Percent changes in SLEDAI-2K scores from baseline to week 14 and at week 28
- Flare rate and severity at week 14 and week 28 based on BILAG index A or B (flare is defined as the presence of 1 or more new BILAG A scores or 2 or more new BILAG B scores.)
- Time to first flare
- Number of patients requiring an increase in oral glucocorticosteroid dose before week 14
- Physician's Global Assessment at week 14 and week 28
- Fatigue (FACIT-F) and SF-36v2 Physical Component Score (PCS) at week 14 and week 28
- ECLAM at week 14 and week 28

Efficacy endpoints will be summarized using descriptive statistics by visit and treatment group. Change from baseline will be calculated as post-baseline value minus baseline value. Percentage change from baseline will be calculated as (post-baseline value – baseline value)/baseline value ×100(%). Efficacy analysis will be performed on the ITT and PP populations.

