16.3.1 Deviations from the Study Protocol

Deviations from the protocol will be listed during the study and/or when an individual subject's eCRF is completed (monitored).

Before unblinding the data for interim and final analysis, a blinded data review meeting (BDRM) will take place where protocol deviations will be classified (major/minor protocol deviations) for statistical analysis.

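### The per-protocol set keeps subjects who stop early for a possibly drug-related event but has no place for those who stop for a lupus flare or lack of efficacy judged unrelated, so membership depends on the outcome being analysed

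*Protocol*

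**What the plan says.** Section 15.2.1 of the protocol builds the PP set from the ITT set. It admits subjects "who finish the study without major protocol deviations or who discontinue the trial prematurely due to an event which could be possibly related" to study medication, and adds: "Subjects with major protocol deviations will be excluded from the PP population". Those are the only two ways in.

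Section 14.3.1 allows a worsening of the underlying condition to be recorded as an adverse event. Its causality categories are related and not related, and one of the examples under not related is "expected progression of underlying or concomitant disease".

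Section 15.2.5 states: "Efficacy analysis will be performed on the ITT and PP populations". Its endpoints include 50% improvement in joints or CLASI at weeks 14 and 28, flare rate and severity, time to first flare, and "Number of patients requiring an increase in oral glucocorticosteroid dose before week 14". It does not say which set leads. The ITT set requires only a dose of study medication and one post-baseline efficacy value, so flare, rescue or withdrawal does not remove anyone from it.

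**The concern.** A PP set normally removes subjects whose data say little about the treatment as planned. A subject who stops because lupus is uncontrolled is a different case, because the stop is itself evidence of failure. Under section 15.2.1, two subjects who stop at the same visit are treated differently: one with a possible drug reaction stays, and one with a flare put down to the disease leaves. The flare and steroid endpoints then lose the subjects in whom those events were most serious, and the response endpoint loses likely non-responders from its denominator.

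This is a stated rule and not a detail left for the SAP. It also turns on the investigator's causality call, which was not designed to decide who counts in an efficacy table. With 6 placebo subjects per part and no formal tests, readers will compare tables by eye. The interim efficacy summaries also go to the DSMB that recommends the Part II dose (sections 8.1 and 15.2.8).

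**Working it through.** **Step 1: trace the rule.** Take a subject in the ITT set with no major deviation.

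| What happens | Finishes the study? | Stopping event possibly related? | In PP? |
|---|---|---|---|
| Completes to week 28 | yes | not applicable | yes |
| Stops for a possible drug reaction | no | yes | yes |
| Stops for a flare judged possibly related | no | yes | yes |
| Stops for a flare judged to be disease progression | no | no | no |
| Completes treatment, then stops for such a flare between weeks 14 and 28 | no | no | no, and the week 14 result goes too |

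The last two rows are the defect. The third row shows that the exclusion depends on the causality call and is not absolute.

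**Step 2: the plan's own figure.** The planned size is 2 parts × (12 + 6) = 36, which agrees with sections 12.1.1 and 15.1. Section 15.1 gives no statistical basis for it. The protocol gives no responder, flare or withdrawal rate, so the rest is an illustration on assumed counts.

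**Step 3: possible size.** From section 9: 12 BT063 and 6 placebo in one part. Assumed: 6 responders on BT063, 2 on placebo, and all flare withdrawals judged unrelated and non-responders. With r responders, n subjects and f such withdrawals in an arm, the ITT rate is r/n and the PP rate is r/(n − f).

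ITT: 6/12 − 2/6 = 50.0% − 33.3% = 16.7 points.

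| Leaving PP (BT063, placebo) | PP rates | PP difference |
|---|---|---|
| 1, 1 | 6/11 = 54.5%; 2/5 = 40.0% | 14.5 points |
| 1, 2 | 6/11 = 54.5%; 2/4 = 50.0% | 4.5 points |
| 0, 2 | 6/12 = 50.0%; 2/4 = 50.0% | 0 points |
| 2, 1 | 6/10 = 60.0%; 2/5 = 40.0% | 20.0 points |
| 3, 1 | 6/9 = 66.7%; 2/5 = 40.0% | 26.7 points |

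If the same subjects stay in as non-responders, the difference is 16.7 points in every row. The five patterns are examples and not bounds. Three leaving BT063 and none leaving placebo would give 6/9 − 2/6 = 33.3 points. A subject who responded at week 14 and then left in follow-up would lower the PP rate in that arm at week 14, not raise it.

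**The case against.** The strongest reply is that little rests on the PP set. The primary endpoint is adverse events, analysed on the safety set. Efficacy is secondary, descriptive and untested. ITT keeps every one of these subjects who has a post-baseline efficacy value, and the interim package includes individual listings, so the DSMB can see each withdrawal. That stands, and it limits the weight of the point.

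It can also be said that a flare stop is not bound to leave PP. Section 14.3.1 classes an event as related when a reasonable possibility cannot be excluded, investigators are blinded, and section 12.4 does not name flare among its example reasons for withdrawal. This is right, and it is why the point covers only stops judged unrelated. It does not rescue the rule, because set membership still follows a causality opinion about an efficacy outcome.

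Four stronger readings are tempting but not supported:

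- *PP drops everyone who needs disallowed rescue.* The protocol does not say so. Table 11.1 permits some rescue: "At most two short courses of an increased dose of oral glucocorticosteroids (i.e., 5 days) are allowed between week 4 and week 12". Whether use beyond that is a major deviation is left open: "Classification of protocol deviations as major or minor will be agreed upon between Sponsor and study statistician prior to the analysis". Section 16.3.1 places the decision at a blinded data review meeting, where "protocol deviations will be classified (major/minor protocol deviations) for statistical analysis". Keeping users of restricted drugs in a PP set is a genuine trade-off and no part of this point.
- *The bias always runs against the drug.* The table in the working shows the difference shrinking or growing.
- *Each placebo subject lost moves the response rate by 17 points.* One subject is 1/6 = 17% of the arm, but losing one non-responder moves 2/6 to 2/5, which is 6.7 points. It takes two to reach 2/4, a shift of 16.7.
- *The steroid-increase endpoint would empty out in PP.* Subjects who have a permitted course and finish stay in PP and count.

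**Conclusion.** The point holds in limited form. Section 15.2.1, read with section 14.3.1, excludes from PP any withdrawal for flare or lack of efficacy judged unrelated, while it keeps withdrawals judged possibly drug-related. Since section 15.2.5 analyses flare, steroid increase and response on PP, that set selects on outcome, and its results can be biased in either direction. In the illustration, an ITT difference of 16.7 points becomes 0 to 26.7 in PP across the five patterns. This rests on assumed responder and withdrawal counts, one part's planned arm sizes, and withdrawals that are all non-responders. The protocol gives no rates from which to say which pattern is likely. No test or primary result is affected. It is worth correcting because the plan orders the PP analysis, does not rank it below ITT, and has few enough subjects for one or two exclusions to change the picture.

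**What to change.** In section 15.2.1, extend the second route into PP to subjects who discontinue for flare, disease worsening or lack of efficacy, whatever the causality assessment, provided they have no other major deviation. State that they count as non-responders at response assessments falling after they stop, that a week 14 result obtained before a follow-up withdrawal is kept, and that their flare and steroid-increase events are counted. Say that this takes precedence over the optional LOCF in section 15.2.2 for the response endpoint. In section 15.2.5, name ITT as the leading efficacy set and PP as supportive.

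The cost is a few sentences. PP becomes slightly larger and closer to ITT, so the two tables will differ less. No treatment, visit or withdrawal rule changes, and the classification of disallowed rescue stays with the blinded data review.

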15.2.2 General Methodology

Descriptive statistics will be presented for all parameters of interest. Continuous variables will be summarized using the n, mean, standard deviation (SD), median, minimum value, and maximum value. Categorical variables will be summarized using the sample size (N), frequency count (n), and percentage (%). All summary tables will be presented by treatment group, unless otherwise specified. For all parameters of interest, the value that was obtained just prior to the first dose of study drug will be used as the baseline.

No formal statistical tests will be performed. Last observation carried forward (LOCF) imputations for efficacy analysis may be used to impute missing data, if appropriate.

15.2.3 Demographic Data and other Baseline Characteristics

The demographic data such as age, sex, race, ethnic origin, height, and weight will be summarised by treatment group using summary statistics. Other baseline disease characteristics will be tabulated and summarized as well.

15.2.4 Safety Analysis

The safety assessments for this study are the following:

- Adverse events (Including SAEs and AEs leading to discontinuation due to AEs)
- Physical examinations
- Vital signs
- ECGs
- Safety laboratory parameters (full blood count including white differential count, clinical chemistry, thyroid hormones, urinalysis, and faecal occult blood test)
- Development of anti-drug antibodies against BT063 (anti-BT063)
- Immunological status of potential viral and bacterial infections (HBV, HCV, HIV, tetanus, diphtheria tuberculosis)
- EBV / CMV Serology
- Premature withdrawals

Adverse events will be coded using the latest available version of the Medical Dictionary for Regulatory Activities (MedDRA®). Incidence rates (i.e., number and percentage of affected subjects) will be calculated for the coding levels system organ class and preferred term. Further analyses of AEs will focus on seriousness, intensity, causal relationship to study medication, and outcome. Serious adverse events will be displayed in detail.

Safety laboratory assessments will be categorized with respect to the laboratory specific reference ranges as normal/abnormal. Abnormal values will be further classified with respect to clinical relevance. Changes over time will be described by means of "shift-tables".

Observed values and change from baseline in 12-lead ECG parameters will be presented by treatment group. The number and percentage of subjects who had an overall impression status in category of normal, abnormal not significant, or abnormal significant will be summarized by treatment group.

Vitals signs parameters (systolic blood pressure, diastolic pressure, heart rate, and temperature) will be presented as a summary of observed and change from baseline values. Summaries for vital signs will be presented by visit and treatment group.

Safety analysis will be based on the safety population.

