The hyperactivity of B-lymphocytes plays a key role with massive abnormal production of immunoglobulin (Ig) G auto-antibodies (95% of patients with anti-nuclear auto-antibodies [ANA], 70% with auto-antibodies against double-stranded DNA [anti-dsDNA]). This pathological process results in sequestration and destruction of Ig-coated cells, fixation and cleaving of complement proteins, and release of chemotaxins, vasoactive peptides, and destructive enzymes into tissues. Most of the auto-antibody profiles/types are characteristic for each person at the time of clinical manifestations (Hahn 2005).

In the course of the entire disease, the vast majority (95%) of patients suffer from systemic symptoms such as fatigue, malaise, fever, anorexia, and weight loss, which are present most of the time. During the course of SLE, a total of 95% of patients complain of musculoskeletal disease (symptoms of arthralgia and myalgia, non-erosive polyarthritis, and myositis), 80% have cutaneous lesions (photosensitivity, malar rash, alopecia, and discoid rash), 85% report haematological disease (chronic anaemia, leukopenia, and lymphopenia), 60% have neurological disorders (cognitive, mood, and headache), 60% experience cardiopulmonary disease (pleurisy, pericarditis, and

effusions), 30 to 50% have renal disease, 40% report gastrointestinal disease, 15% report thrombosis and 15% experience ocular disease ([Bertsias](#) et al 2012).

Most patients experience periods of flares alternating with remissions. Permanent remissions (absence of symptoms with no treatment) are very rare. Nowadays, 10-year survival is over 90% mainly based on earlier diagnoses, as well as symptomatic treatment with anti-inflammatory and immune-suppressive medications.

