12.3 Exclusion Criteria

Subjects having any of the following criteria, either at screening or at baseline, will not be included in the study:

Exclusion Criteria	Rationale	Screening	Baseline
1. Has active, severe SLE disease activity which involves the renal system and/or active, severe, neuropsychiatric SLE, defined as any neuropsychiatric element scoring BILAG level A disease.	Medical	•	•
2. Diagnosed psoriasis	Medical	•	
3. Presence or history of malignancy within the previous 5 years (except for successfully treated non-metastatic cutaneous squamous or basal cell carcinoma and/or localized carcinoma in situ of the cervix)	Medical	•	
4. Received any vaccination within 8 weeks prior to screening (except for influenza or tetanus booster)	Medical	•	

Exclusion Criteria	Rationale	Screening	Baseline
5. History of more than 3 infections during the last 12 months requiring IV antibiotic treatment	Medical	•	
6. Systemic antibiotic treatment within 2 weeks before the baseline visit	Medical		•
7. A positive diagnosis for any of the following: 
 • Acute or chronic viral hepatitis B (isolated positivity to hepatitis B surface antibody [anti-HBs] is allowed as an indicator of a previous vaccination that will be confirmed in the subject's notes) or acute or chronic hepatitis C (positive to anti-hepatitis C antibodies or hepatitis C viral RNA) • Human immunodeficiency virus (HIV) or tested positive for tuberculosis as assessed by QuantiFERON® TB gold test (if the result is inconclusive it may be repeated once) • Acute, clinically relevant, or potentially recent infection with Herpes Zoster or Herpes Simplex (Type 1 and Type 2), EBV or CMV infection or reactivation at screening 	Medical	•	
8. Clinically significant hematologic abnormalities attributed to SLE: 
 • Haemoglobin < 8 g/dL • Platelets 50×10^9/L • Leucocytes $< 2 \times 10^9$/L 	Medical	•	
9. Active or history of inflammatory bowel disease (including active or history of colitis)	Medical	•	

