14.1.2.3 Laboratory Parameters

The tests listed in Table 14.1 will be conducted on samples collected and analysed by standard laboratory procedures at the time points designated on the Flowchart of the Study (Section 3). Tests that are not done must be reported as such on the eCRFs. Subjects should not eat or drink anything except water for 12 hours before the fasting glucose and fasting lipid tests at Visits 1, 2, and 12.

Sample handling, shipment, and assessment methods are described in the laboratory manual.

Table 14.1: Clinical Laboratory Tests

Haematology		
Haematocrit	White blood cell count with differential (neutrophils, eosinophils, lymphocytes, basophils, monocytes)	Coagulation (fibrinogen, prothrombin time, partial thromboplastin time)
Clinical Chemistry		
Alanine aminotransferase	Lipase	Urea
Aspartate aminotransferase	Bilirubin	Sodium
Gamma glutamyl transferase	Total protein	Chloride
Alkaline phosphatase	Albumin	Potassium
Lactic dehydrogenase	Creatinine	Calcium
ESR	CRP	
Urinalysis		
pH	Glucose	Urobilinogen
Blood	Ketones	Nitrites
Leucocytes	Bilirubin	Specific gravity
Protein		Microscopy

Table 14.1: Clinical Laboratory Tests

Other tests		
Thyroid stimulating hormone	Hepatitis B virus (hepatitis B virus polymerase chain reaction, hepatitis B surface antigen, hepatitis B surface antibody, total hepatitis B core antibody)	Tetanus (tetanus IgG antibodies, QuantiFERON®-TB Gold in-tube assay)
Free triiodothyronine		Diphtheria (IgG)
Free thyroxine		Epstein-Barr virus
Fasting glucose		Cytomegalovirus
Fasting triglycerides		
Fasting total cholesterol		Faecal occult blood test
Fasting high-density lipoprotein	Hepatitis C (hepatitis C polymerase chain reaction, hepatitis C viral RNA)	Pregnancy test or FSH assessment (females only)
Fasting low-density lipoprotein	HIV (anti-HIV1, anti-HIV2)	

All laboratory results have to be evaluated and results reported on the eCRF according to the following pattern:

- Outside reference range but not clinically relevant (e.g., due to already known conditions, due to sampling conditions, only marginal deviation, due to underlying diseases in the study population)
- Outside reference range and clinically relevant.

Laboratory values which are outside the reference range and assessed as clinically relevant) must be documented as AEs if they occur for the first time after administration of IMP.

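### The laboratory shift tables in Section 15.2.4 carry no direction and no grade, so worsening within a class and a move from low to high do not show

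*Protocol*

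**What the plan says.** The laboratory method is in Section 15.2.4 (Safety Analysis). Its first step is: "Safety laboratory assessments will be categorized with respect to the laboratory specific reference ranges as normal/abnormal". The next sentence adds a second step: "Abnormal values will be further classified with respect to clinical relevance". Changes over time are then assigned to shift tables.

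Section 14.1.2.3 (Laboratory Parameters) sets up the same two abnormal classes for the eCRF. One is "Outside reference range and clinically relevant". The other is outside the range but not clinically relevant, and the examples given for it include "only marginal deviation, due to underlying diseases in the study population".

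For ECG parameters and vital signs, Section 15.2.4 names observed values and change from baseline. It does not do so for laboratory values.

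Exclusion criterion 8 in Section 12.3 ("Clinically significant hematologic abnormalities attributed to SLE") sets three limits: haemoglobin 8 g/dL, platelets 50 x10^9/L and leucocytes 2 x10^9/L. The platelet limit is read here as below 50, as the synopsis has it. Criterion 18 also lets the investigator exclude a subject for any other significant laboratory abnormality that might compromise safety or influence the outcome.

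**The concern.** Safety and tolerability are the primary objective of both parts, and no tests are planned, so the descriptive display is the analysis. A shift table can show only what its classes distinguish. Here they distinguish in range from out of range and, among out-of-range values, the investigator's view of relevance. In lupus, a blood count can be out of range before the first dose. For that subject and parameter, a further fall changes class only through a judgement, and underlying disease is an accepted reason to leave the value as not relevant.

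Direction matters as well. Appendix B lists low leucocyte and platelet counts as features of the disease, while Section 11.1.3 reports minimal transient platelet rises at the highest dose in the repeated-dose monkey study. A table that puts low and high in one class cannot tell these apart.

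The interim safety tables go to the DSMB, which recommends the Part II dose.

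**Working it through.** The plan states no figure that could be reproduced here, so the check is one of logic with worked values.

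**Step 1: who can start abnormal.** Criterion 8 excludes leucocytes below 2.0 and platelets below 50 x10^9/L. Appendix B counts leucocytes below 4,000/mm3 (4.0 x10^9/L) and platelets below 100,000/mm3 (100 x10^9/L) as haematologic disorder. Criterion 8 therefore admits leucocytes from 2.0 up to 4.0 and platelets from 50 up to 100 x10^9/L, subject to criterion 18.

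**Step 2: what each scheme shows.** The protocol gives no reference range for leucocytes. Assume 4 to 10 x10^9/L for illustration. The example values are also illustrative, and every baseline value below is at or above 2.0. Change is the later value minus baseline.

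| Leucocytes (x10^9/L) | Normal/abnormal | With the relevance split | Low/normal/high | Change |
|---|---|---|---|---|
| 5 to 2.1 | normal to abnormal | shift shown | normal to low | 2.1 - 5 = -2.9 |
| 3.9 to 2.1 | abnormal to abnormal | shift only if the rating changes | low to low | 2.1 - 3.9 = -1.8 |
| 3.5 to 1.8 | abnormal to abnormal | shift only if the rating changes | low to low, newly below 2.0 | 1.8 - 3.5 = -1.7 |
| 3.4 to 11.5 | abnormal to abnormal | reversal of direction not shown | low to high | 11.5 - 3.4 = +8.1 |

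**Step 3: reading the table.**
- A subject who starts in range is served adequately by the plan's scheme (row 1).
- A subject who starts low can worsen, even past the trial's own entry limit (row 3), with no shift unless the rating moves from not relevant to relevant. Nothing in the protocol ties that rating to a numerical limit.
- A reversal of direction (row 4) cannot be read from the plan's classes whatever the rating.
- Low/normal/high classes alone repair row 4 but not rows 2 and 3. Row 3 also needs a count against a limit, and row 2 needs the change from baseline. This is why the fix has three parts.

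**The case against.** The strongest reply is that the shift table is not the only laboratory output.
- Section 15.2.2 promises n, mean, SD, median, minimum and maximum by treatment group for all parameters of interest.
- The synopsis lists change from baseline through week 14 in safety laboratory parameters among the endpoints. If that change is summarised with the Section 15.2.2 statistics, its minimum shows the largest single fall in each arm.
- Section 14.3.2 makes a clinically relevant change from pre-treatment values an adverse event, so an abnormal baseline does not block capture.
- Section 15.2.8 adds individual listings at the interim, where 18 subjects can be read one by one, and Section 8.1 gives the DSMB unblinded data.
- BILAG records blood counts, and SLEDAI-2K scores leukopenia and thrombocytopenia.

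Much of this stands, and it limits the point. What remains is narrower. Minimum and maximum describe one extreme subject, not how many worsened or from where. Section 15.2.4 itself gives laboratory change to shift tables and names change from baseline only for ECG and vital signs. Adverse event capture rests on the same relevance judgement, and its two wordings differ: Section 14.1.2.3 asks for first occurrence after dosing, while Section 14.3.2 asks for a relevant change from pre-treatment. Listings do not tabulate by arm. BILAG and SLEDAI-2K are planned as efficacy scores.

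A second reply is that such detail belongs in the SAP, to which Sections 15 and 15.2.9 defer. An SAP may well add direction and worst values. But the protocol has already named the classes and the display, so this is a comment on a stated choice and not on a missing detail.

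A reader might also infer a size from the Introduction: "85% report haematological disease (chronic anaemia, leukopenia, and lymphopenia". Then 0.85 x 12 = 10.2, or about 10 of the 12 BT063 subjects in a part, would have an uninformative table. The documents do not support this. The figure covers the course of the disease, not trial baseline, and it pools several abnormalities. Shift tables are usually built per parameter, so a subject with low lymphocytes can still shift on platelets. The relevance split lets some abnormal subjects shift too.

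**Conclusion.** The point holds as a weakness of the stated display. The three classes have no direction and no grade. Subjects with mild to moderate cytopenia can be enrolled. For them, worsening within a class and a move from low to high do not appear in the shift table, and a move between the two abnormal classes depends on judgement. The other planned outputs reduce the loss but do not provide a by-arm display of individual worsening.

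The size cannot be quantified, because the protocol gives no baseline rate of abnormality for any parameter. It would be too strong to say that worsening cytopenia goes unseen in this trial, or that it must read as abnormal to abnormal: a changed relevance rating, an adverse event report or a listing can each reveal it. The conclusion rests on Section 15.2.4 being applied as written; an SAP with directional tables would already meet it. Label: cheap improvement.

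**What to change.** In Section 15.2.4:
1. Replace normal/abnormal by low/normal/high shift tables for each parameter, from baseline to the lowest and to the highest post-baseline value, and keep the clinical-relevance flag.
2. State that observed values and change from baseline are summarised for laboratory parameters by visit and arm, in line with ECG and vital signs and with the synopsis endpoint.
3. Tabulate by arm the number of subjects whose values newly fall below the haematology limits already used in exclusion criterion 8. This is a descriptive count only and implies no rule for managing subjects.

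The laboratory values and reference ranges are already part of the plan, so no new data are needed. The cost is a few more tables to program. With 12 and 6 subjects per part the counts will be small and should be read as description.
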